## 12.2 Deriving and Summarizing Pharmacokinetic Parameters

For subjects belonging to the PK Analysis Set, the PK parameters provided in [Appendix 16.2](#) will be determined from the CSL346 serum concentration-time data.

The PK parameter derivation including imputation of the values BLQ and missing data will be conducted in accordance to (1), (2), (3), and (4) which gives guidance on how to derive PK parameters in the presence of missing data.

PK parameters of CSL346 will be summarized with the following statistics being provided.

Variable	Statistical Parameters:
$C_{\max}$ after IV loading dose, $C_{\max}$ after first SC dose, $C_{\text{trough}}$ after each SC dose, $AUC_{\text{day1}}$ , $AUC_{0-28d}$ , CL after first SC dose	n, arithmetic mean, SD, CV%, minimum, median, maximum, geometric mean and geometric CV%
$T_{\max}$ after IV loading dose, $T_{\max}$ after first SC dose,	n, minimum, median, and maximum

The geometric CV% will be calculated as  $100 \times \sqrt{\text{((anti-log of variance for log transformed data) minus 1)}}$   $CV\% = 100 \times \sqrt{\exp(\ln(SD^2)) - 1}$ .

All PK parameters will be reported to at least 3 significant digits, but to no more significant digits than the precision of the original serum concentration data.

A by-subject listing of CSL346 PK parameters based on the PK Analysis Set will be provided.

### **12.3 Pharmacokinetic Statistical Analyses**

Dose-adjusted PK parameters of  $AUC_{\text{day1}}$ ,  $AUC_{0-28d}$ ,  $C_{\text{max}}$  after IV loading dose, and  $C_{\text{max}}$  after first SC dose will be natural log transformed and analyzed in an analysis of variance model, comparing the 8 mg/kg and 16 mg/kg dose levels. The model will be based on the dose level as the only effect. The estimate and 90% CI for the difference of 16 mg/kg – 8 mg/kg will be exponentiated to obtain the point estimate and CI for the geometric mean ratio. Dose proportionality is supported when the 90% CI includes the 1.

Graphical displays of CSL346 will include a separate display for each natural log transformed PK parameter versus natural log transformed dose to evaluate dose proportionality.

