For the low dose, a loading dose of 3 mg/kg IV, followed by administration of 8 mg/kg SC on Day 1 (Visit 4) and every 4 weeks thereafter, was selected. Trough concentrations at steady state ($C_{\text{trough}_{ss}}$) are predicted to exceed 14.4 $\mu\text{g}/\text{mL}$ in 99.9% of subjects treated with 8 mg/kg through Week 16 (Visit 10) (Figure 2). Predicted median (95% CI) area under the concentration-time curve ($AUC_{0-28d_{ss}}$ (AUC between doses at steady state where dosing interval $[\tau] = 28$ days [4 weeks]) following repeat dosing of 8 mg/kg SC is 1336 (970 to 1921) $\mu\text{g}\cdot\text{day}/\text{mL}$. This exposure is approximately 4.4- (6.0- to 3.0-) fold lower than the mean $AUC_{0-\infty}$ (AUC from time 0 to infinity) exposure after 12 weeks of follow up in healthy volunteers administered a single 20 mg/kg dose (5839 $\mu\text{g}\cdot\text{day}/\text{mL}$) in Study CSL346_1001 (Table 2).

Selection of the high dose was based on the uncertainties of translation of mouse disease models to humans and the lack of quantitative data on VEGF-B levels in human tissues or a validated PD marker. Including a 2-fold higher dose allows for higher local exposure in the kidney and thus, an increased likelihood to observe efficacy in this proof of concept study in case activity is driven by local tissue concentrations of VEGF-B and CSL346 rather than systemic exposure. Additionally, the dose-response relationship across these 2 dose levels will help inform dose selection for a phase 2b dose-finding study.

For this high dose, a loading dose of 6 mg/kg IV will be followed by 16 mg/kg SC on Day 1 (Visit 4) and every 4 weeks thereafter. Following repeat dosing at the high dose of 16 mg/kg,

median (95% CI) $AUC_{0-28d_{ss}}$ is predicted to be 2770 (1931 to 3815) $\mu\text{g}\cdot\text{day}/\text{mL}$. This exposure is approximately 2.1 (3.0 to 1.5) fold lower than the mean $AUC_{0-\infty}$ exposure after 12 weeks of follow up in healthy volunteers administered a single 20 mg/kg dose (5839 $\mu\text{g}\cdot\text{day}/\text{mL}$) in Study CSL346_1001 (Table 2). The trough concentrations at steady state ($C_{\text{trough}_{ss}}$) in subjects treated with 16 mg/kg CSL346 is predicted to exceed 14.4 $\mu\text{g}/\text{mL}$ in all (ie, 100%) subjects at Week 16 (Visit 10) and in 59% of subjects at Week 24 (Visit 11) (Figure 2).

Figure 2 Predicted CSL346 Concentrations Following Monthly SC Dosing with IV Loading Dose

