3.5 Planned Number of Subjects

The study will randomize a target of 100 subjects:

- 25 subjects randomized to the 8 mg/kg CSL346 group
- 25 subjects randomized to the 16 mg/kg CSL346 group

- 50 subjects randomized to the placebo group

A subject is considered enrolled in the study once they have signed the ICF. A subject is considered eligible for randomization into the study when all inclusion criteria have been met, none of the exclusion criteria have been met, and the randomization criteria have been met ([Section 4.1](#)).

The actual early discontinuation rate will be assessed throughout the study and up to 124 subjects may be randomized, if necessary, to target 94 completed subjects (subjects who received all doses and completed the Week 16 ACR assessment).

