10.3.4 Pharmacokinetic Analyses

Secondary Endpoints

Serum concentrations of CSL346 will be listed by individual subject and will be summarized by dose level and nominal time point using descriptive statistics (ie, n, arithmetic mean, SD, CV%, median, geometric mean, geometric CV%, minimum, and maximum). Individual subject CSL346 serum concentration versus time will be plotted on linear and semilogarithmic scales. The C_{trough} of CSL346 will also be summarized visually, by dose level.

PK parameters will be derived using noncompartmental analyses, and will include the following:

- C_{\max} after IV loading dose
- T_{\max} after IV loading dose
- C_{\max} after first SC dose
- T_{\max} after first SC dose
- $AUC_{0-\tau}$
- C_{trough} after each dose

The following descriptive statistics will be presented, by dose level, for all PK parameters, except for T_{\max} , n, arithmetic mean, SD, CV%, median, geometric mean, geometric CV%, minimum, and maximum. The n, median, minimum, and maximum will be summarized for T_{\max} . Additional information on the analyses of PK parameters will be provided in the SAP. These analyses will be performed on the PK Analysis Set.

Dose-adjusted PK exposure parameters will be natural log transformed and analyzed in an analysis of variance model, comparing the 16 mg/kg and 8 mg/kg dose levels. The estimate and 90% CI for the difference of 16 mg/kg – 8 mg/kg will be exponentiated to obtain the point estimate and CI for the geometric mean ratio. The point estimate and CI will be used to assess dose proportionality.

Exploratory Endpoint

Urine concentration of CSL346 will be listed by individual subject and will be summarized by nominal time point using descriptive statistics. This analysis will be performed on the PK Analysis Set.

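### SAP 12.3 counts a 90% CI that includes 1 as support for dose proportionality, so imprecise data favour the claim and very precise data reject trivial departures

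*SAP*

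**What the plan says.** SAP 12.3 takes four dose-adjusted parameters: AUC on Day 1, AUC over 0 to 28 days, Cmax after the IV loading dose and Cmax after the first SC dose. Each is log-transformed and put through an ANOVA: "The model will be based on the dose level as the only effect". The log-scale contrast of the high dose against the low dose is then back-transformed, with its 90% CI, to a ratio of geometric means. The section closes with the decision rule: "Dose proportionality is supported when the 90% CI includes the 1". No acceptance limits, precision requirement or power accompany the rule. A log-log plot of parameter against dose is also planned, without a criterion.

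Protocol 10.3.4 describes the same comparison but stops earlier: "The point estimate and CI will be used to assess dose proportionality". The pass rule therefore appears only in the SAP, and SAP Section 5 does not list it among the changes from the protocol.

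Protocol 3.5 sets the arm sizes: "25 subjects randomized to the 8 mg/kg CSL346 group" and "25 subjects randomized to the 16 mg/kg CSL346 group".

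**The concern.** The 90% CI includes 1 exactly when a two-sided 10% test fails to reject a ratio of 1. The SAP reads that non-rejection as positive support. The null hypothesis is proportionality itself, so anything that weakens the test (fewer evaluable subjects, larger between-subject spread) raises the chance of the favourable verdict. When the data are very precise, the same rule declares against proportionality for departures too small to matter.

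At stake is whether the one-word PK conclusion can be trusted. A reader who takes the verdict at face value could be told that exposure scales with dose because the data were too noisy to show otherwise, or that it does not because the data were good.

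**Working it through.** The documents give no power, margin or expected precision for this analysis, so there is no figure of the plan's own to reproduce.

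**Inputs**

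- n = 25 per dose (Protocol 3.5).
- One-way ANOVA on two groups, which is a pooled two-sample t with 2 × 25 − 2 = 48 df (SAP 12.3). The 90% CI uses t(0.95, 48) = 1.677.
- Between-subject spread. The only PK spread in the documents is the predicted steady-state AUC in Protocol 3.3.2: for the low dose "following repeat dosing of 8 mg/kg SC is 1336 (970 to 1921") and for the high dose "is predicted to be 2770 (1931 to 3815"). If these are read as 95% between-subject intervals, the log SD is ln(1921/970)/(2 × 1.96) = 0.174 and ln(3815/1931)/(2 × 1.96) = 0.174. The CV is √(exp(0.174²) − 1), about 17.6%.
- CVs of 30%, 40% and 50% are assumptions, because no spread is given for subjects with DKD.

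**Formula**

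For true ratio R and SD = √ln(1 + CV²), the standard error is SE = SD × √(2/25). The chance that the rule says supported is P(|T| ≤ 1.677), where T is noncentral t with 48 df and noncentrality ln(R)/SE.

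**Result for a true ratio of 1.25** (ln 1.25 = 0.2231)

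| CV | SD | SE | Noncentrality | Called supported | CI factor exp(1.677 × SE) |
|---|---|---|---|---|---|
| 17.6% | 0.175 | 0.0494 | 4.52 | 0.2% | 1.086 |
| 30% | 0.294 | 0.0830 | 2.69 | 16% | 1.149 |
| 40% | 0.385 | 0.1090 | 2.05 | 35% | 1.201 |
| 50% | 0.472 | 0.1336 | 1.67 | 50% | 1.251 |

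A true ratio of 0.80 gives the same figures by symmetry.

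**Effect of sample size.** At an assumed CV of 40% and a true ratio of 1.25, the chance of a supportive verdict is 0.7% with 100 per dose, 11% with 50 and 35% with 25. Only 25 is planned; the others show the direction. Fewer subjects help the claim.

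**The opposite fault.** At a CV of 17.6% and 25 per dose, a true ratio of 1.05 passes 74.5% of the time and so fails about 25%. A true ratio of 1.10 passes 39.8% and so fails 60%. When R is exactly 1, the rule fails 10% of the time for each parameter at any sample size or CV, because that is the level of the test.

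**What the rule accepts and rejects.** Using the CI factors above, at a CV of 50% an observed ratio of 1.24 has a CI of 1.24/1.251 to 1.24 × 1.251, or 0.99 to 1.55, and is called supported. At a CV of 17.6% an observed ratio of 1.09 has a CI from just above 1 to 1.18 and is not called supported, although it is the tighter evidence and lies closer to 1.

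**The case against.** The best defence is that little depends on the verdict. Dose proportionality is not a listed objective or endpoint, and the primary ACR test is untouched. The ratio and its 90% CI are reported whatever the verdict, a plot is planned, and population PK is analysed and reported separately, so imprecision will be visible. Phase 1 exposure was already described as dose proportional, and the SAP's word is supported, not proven. All of this stands and limits the seriousness. It does not repair a rule that returns the wrong word.

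A second defence concerns size. At the only spread derivable from the documents, a 25% departure is almost never missed. That also stands, with two qualifications: the interval is a steady-state prediction modelled from healthy volunteers, and reading it as between-subject spread is an assumption. At that same spread the rule errs the other way, rejecting small departures.

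Three stronger readings might be inferred, and the documents do not support them.

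- That the verdict will steer phase 2b dose selection. Protocol 3.3.1 and 3.3.2 refer to PK/PD data in general and to the dose-response relationship. No section ties a development decision to the proportionality verdict.
- That far fewer than 25 per dose will be evaluable. The four parameters need samples only through Day 29, the assumed drop-out is 6%, and randomization may rise to 124. Stopping the 16 mg/kg level early would shrink only that arm.
- That false support is the likely outcome. It becomes common only at the higher, assumed CVs.

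**Conclusion.** The rule in SAP 12.3 is wrong as written, whatever the variability turns out to be; only the direction and size of the error depend on the CV. With 25 per dose, the chance of calling a true 25% departure supported runs from 0.2% to 50% over CVs of 17.6% to 50%. The low end rests on reading the Protocol 3.3.2 interval as between-subject spread, and the rest on assumed CVs. At the low end, the chance of failing a true ratio of 1.05 to 1.10 is 25% to 60%. The effect is confined to a descriptive PK statement. The correction is worth making because it is cheap and because the SAP adds a verdict that the protocol did not call for.

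**What to change.** Delete the sentence and report the dose-adjusted ratio with its 90% CI and the plot, without a pass or fail verdict. This is what Protocol 10.3.4 already provides.

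If a verdict is wanted, conclude proportionality only when the whole 90% CI lies inside limits that the sponsor states and justifies before the interim unblinding in SAP 4.5.1, and list the rule in SAP Section 5. The documents contain no margin, and the choice matters. Simulated with 25 per dose, purely as illustration:

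| Limits | True ratio | CV 17.6% | CV 30% | CV 40% | CV 50% |
|---|---|---|---|---|---|
| 0.80 to 1.25 | 1.00 | 99.5% | 69% | 29% | 5% |
| 0.70 to 1.43 | 1.00 | about 100% | 99% | 89% | 68% |
| 0.70 to 1.43 | 1.25 | 85% | 48% | 33% | not run |

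Under 0.80 to 1.25, a true ratio of 1.25 passes at most about 5% of the time at any of these CVs. The wider limits treat 1.25 as acceptable and so do not guard against it. A sponsor who regards a 25% departure as important could not use them.

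The cost is one SAP sentence, with no new data or subjects. The downside is that a positive proportionality statement is no longer automatic, and under tight limits it may be out of reach if spread is large.

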## **13 Pharmacodynamic and Biomarkers Analyses**

Unless otherwise specified, these analyses will be based on the PD Analysis Set.

### **13.1 Biomarker Analyses**

Analysis of biomarker is included in efficacy analysis, please refer to [Section 10.3](#).

## **14 Pharmacokinetic/Pharmacodynamic Analyses**

A correlation plot  $AUC_{0-28d}$  versus baseline ACR will be provided. The Spearman correlation coefficient, a regression line, and slope and intercept of regression will be added to the plot. The same plot will be provided for CL versus baseline ACR and for  $AUC_{0-28d}$  versus baseline eGFR and for CL versus baseline eGFR.

A correlation plot of  $C_{\text{trough}}$  on Day 29 versus change from baseline in ACR at Day 29 will be provided. The Spearman correlation coefficient, a regression line, and slope and intercept of regression will be added to the plot. The same plot will be provided for the assessment at Days 57, 85, and 113. A similar plot will be provided for CL versus change from baseline in eGFR on Day 29.

A correlation plot of urine CSL346 concentration on Day 8 versus baseline ACR on Day 8 will be provided. The Spearman correlation coefficient, a regression line, and slope and intercept of regression will be added to the plot. The same plot will be provided for urine CSL346

concentration at Day 85 versus ACR at Day 85. A correlation plot of urine CSL346 concentration at Day 85 versus change from baseline in ACR at Day 85 will also be provided. The same series of plots will be provided for urine CSL346 concentration versus baseline eGFR and urine CSL346 concentration versus the change in eGFR.

The correlation of systolic blood pressure, measured at 60min after SC dosing at Visit 4, versus  $AUC_{day1}$ , starting after IV administration, will be presented. The Spearman correlation coefficient, a regression line, and slope and intercept of regression will be added to the plot. The same plot will be provided for diastolic blood pressure.

A correlation plot of systolic blood pressure versus  $C_{trough}$  at Day 29 will be provided. The Spearman correlation coefficient, a regression line, and slope and intercept of regression will be added to the plot. The same plot will be provided for the assessments at Days 57, 85, and 113. A similar series of plots will be provided for diastolic blood pressure versus  $C_{trough}$  at Days 29, 57, 85, and 113.

A correlation plot of change from baseline in total cholesterol versus  $C_{trough}$  at Day 29 will be provided. The Spearman correlation coefficient, a regression line, and slope and intercept of regression will be added to the plot. The same plot will be provided for assessments at Days 57, 85, and 113. The same series of plots will be provided for all other biomarkers.

A population PKPD analysis may be used to further assess characterization of PK versus PD endpoints. If such an analysis will be done, this work will have a separate analysis plan and report.

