1.2.3 Clinical Experience

The first in-human clinical study, CSL346_1001, a phase 1, randomized, double-blind, placebo-controlled single ascending dose study to evaluate the safety, tolerability, and pharmacokinetics (PK) of CSL346 in healthy Caucasian and Japanese adult subjects was completed in May 2019. Overall, no AEs of concern occurred following administration of single doses of CSL346 by an IV infusion (up to 20 mg/kg) or SC injection (up to 10 mg/kg) to 60 healthy volunteers, thus demonstrating safety and tolerability up to the maximum exposures achieved. The PK profile suggests dose proportionality and, as expected, is similar in Caucasian and Japanese subjects. The bioavailability after SC administration is estimated to be 61% in healthy volunteers. This study is supportive of continued development of CSL346, including administration of repeat doses of up to 16 mg/kg SC to subjects with DKD.

A detailed description of the safety and PK profile of CSL346 in healthy adult subjects is provided in the Investigator's Brochure.

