An overview of identified and potential risks and planned risk mitigation in this phase 2a study is provided in Table 1.

Table 1 Risks and Risk Mitigation

Risk	Potential/ Identified	Source	Risk Mitigation
Injection site reactions	Identified	CSL346_1001 data on file	
 Assessment at study visits Guidance for managing local intolerance
Hypersensitivity / anaphylaxis and infusion reactions; antibody formation	Potential	Class effect of humanized proteins	
 Standard measures Measurement of baseline, mid-, and end of study anti-CSL346 antibody
Weight gain	Potential	Knock-out mouse model [Hagberg et al, 2010]	
 Monitor at study visits
Congenital disorders	Potential	Knock-out mouse model [Bellomo et al, 2000] Preclinical study in quails [Tomanek et al, 2006]	
 Inclusion / exclusion criteria Contraception requirements Pregnancy testing Nonclinical studies in later phases
Renal: acute reversible effect on GFR and / or chronic kidney injury	Potential	Theoretical risk due to VEGF-A modulation [Kamarzarian et al, 2018; Izzedine et al, 2010]	
 Inclusion / exclusion criteria Staged approach for enrollment of subjects with moderate renal impairment Frequent monitoring in first 4 weeks of treatment Measure SCr and evaluate albuminuria at each visit Guidance for managing increases in SCr and albuminuria

Risk	Potential/Identified	Source	Risk Mitigation
Cardiac: myocardial dysfunction with chronic dosing	Potential	Knock-out mouse model [Bellomo et al, 2000] Streptozotocin model [Lal et al, 2017] Theoretical risk due to VEGF-A modulation [Touyz et al, 2018]	
 Exclusion criteria, including baseline assessment of LVEF by ECHO Treatment with SOC Baseline and periodic ECG, BNP, and troponin levels Guidance for managing increases in troponin levels
Increased BP	Potential	Theoretical risk due to VEGF-A modulation [Touyz et al, 2018]	
 Exclusion criteria BP measurement Guidance for managing increases in BP

BP = blood pressure; BNP = b-type natriuretic peptide; ECG = electrocardiogram; ECHO = echocardiogram; GFR = glomerular filtration rate; LVEF = left ventricular ejection fraction; SCr = serum creatinine; SOC = standard of care; VEGF = vascular endothelial growth factor.

2 Study Objectives and Endpoints

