2.3 Exploratory Objectives and Endpoints

2.3.1 Exploratory Objectives

The exploratory objectives of this study are:

1. To explore the effect of CSL346 on the following potential pharmacodynamic (PD) biomarkers:
 - Biomarkers of lipid metabolism
 - Biomarkers of glycemic control
 - Novel plasma, serum, and urinary biomarkers

2. To measure the concentration of CSL346 in the urine and explore its association with albuminuria
3. To explore the relationship between PD biomarkers and CSL346 PK characteristics
4. To evaluate the frequency of subjects with macroalbuminuria (ACR > 300 mg/g [> 33.9 mg/mmol]) at Baseline regressing to microalbuminuria (ACR ≥ 30 and ≤ 300 mg/g [≥ 3.39 and ≤ 33.9 mg/mmol]) or normoalbuminuria (ACR < 30 mg/g [< 3.39 mg/mmol]), or from microalbuminuria to normoalbuminuria
5. To explore possible dose response for the primary and secondary efficacy and safety endpoints

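### The only serum-PK plot for change in eGFR uses clearance, which is nearly the same at both doses, so an exposure-related fall in eGFR would be largely hidden in that display.

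*SAP*

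**What the plan says.** SAP section 14 sets out the PK/PD plots, each with a Spearman coefficient and a fitted line.

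- **ACR.** Trough concentration is plotted "on Day 29 versus change from baseline in ACR at Day 29 will be provided", and then: "The same plot will be provided for the assessment at Days 57, 85, and 113".
- **Blood pressure.** Systolic and diastolic pressure are plotted against trough at the same four days.
- **Biomarkers.** Change in total cholesterol is plotted against trough at the same four days, and the series is extended to all other biomarkers.
- **eGFR, serum PK.** "A similar plot will be provided for CL versus change from baseline in eGFR on Day 29". The remaining serum plots take AUC over 28 days "versus baseline eGFR and for CL versus baseline eGFR", so they concern renal function at entry and not its change.
- **eGFR, urine.** There is a plot of "urine CSL346 concentration versus the change in eGFR".
- **Serum creatinine.** No exposure plot is named.

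The protocol supplies the context. Section 1.2.3 says of phase 1: "The PK profile suggests dose proportionality". Table 1 in section 1.4 lists as a potential risk "Renal: acute reversible effect on GFR and / or chronic kidney injury". Section 2.3.1 includes the objective "To explore possible dose response for the primary and secondary efficacy and safety endpoints".

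**The concern.** A plot meant to reveal an exposure-related effect needs exposure on its axis. Clearance is what remains after exposure has been divided into dose. If PK is dose proportional, subjects on 8 and 16 mg/kg share one distribution of clearance, and the contrast that the higher dose was added to create disappears from the axis.

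What remains is the variation between subjects within a dose, with the sign reversed: low clearance means high exposure, so an adverse effect on eGFR would appear as a weak positive slope. That slope has a second explanation, because subjects whose renal function is falling might eliminate the antibody more slowly.

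eGFR is a key secondary endpoint in the SAP, and an effect on GFR is a named risk. A flat clearance plot with a coefficient near zero could be taken as reassurance that it cannot give.

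**Working it through.** **Inputs.** Protocol section 3.3.2 predicts steady-state AUC of 1336 (970 to 1921) µg·day/mL at 8 mg/kg and 2770 (1931 to 3815) at 16 mg/kg; Table 2 prints 2720 for the latter. The phase 1 reference is 5839 µg·day/mL after a single 20 mg/kg dose. Planned active subjects: 25 + 25 = 50 (section 3.5).

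**The plan's own figures.** The AUC safety margins are 5839/1336 = 4.37 and 5839/2770 = 2.11 (2.15 with 2720). These agree with the stated 4.4 and 2.1.

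**Does clearance depend on dose?** Apparent clearance = dose/AUC.

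- 8 mg/kg: 8/1336 = 5.99 mL/day/kg
- 16 mg/kg: 16/2770 = 5.78 mL/day/kg (16/2720 = 5.88)

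The two differ by 2% to 4%. AUC differs by 2770/1336 = 2.07-fold (2.04 with 2720).

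**How much of the exposure variation is dose?** Read the stated 95% range as between-subject spread (an assumption; the Figure 2 footnote describes 95% prediction intervals from 1000 simulations).

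- Within-dose SD of log AUC = ln(1921/970)/3.92 = 0.174; the 16 mg/kg range also gives 0.174.
- Between-dose SD with equal groups = ln(2)/2 = 0.347.
- Dose share of variance = 0.347²/(0.347² + 0.174²) = 0.120/(0.120 + 0.030) = 0.80.

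With an assumed within-dose SD of 0.30 or 0.40 the share is 57% or 43%. The clearance axis drops this share. A correlation with log exposure shrinks by √(1 − 0.80) ≈ 0.45, so −0.40 on exposure becomes about +0.18 on clearance.

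**Illustration of size.** Simulated Spearman tests, n = 50, two-sided 0.05, with an assumed correlation of −0.40 between log exposure and eGFR change. The last column is a t-test of 16 against 8 mg/kg on the same data.

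| Within-dose log SD | Clearance axis | 16 vs 8 mg/kg |
|---|---|---|
| 0.174 | 22% | 76% |
| 0.30 | 42% | 59% |
| 0.40 | 53% | 47% |

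On the exposure axis, power is about 82% at SD 0.174. By the Fisher z approximation it is 83%, whatever the SD, because the correlation is fixed on that axis. For assumed correlations of 0.3 to 0.5, the same approximation at SD 0.174 gives 56% to 97% on exposure and 15% to 35% on clearance.

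**A side point on clearance.** With a half-life of about 30 days (protocol 3.3.2) and mono-exponential decline, exp(−ln 2 × 28/30) = 52% of total AUC lies beyond 28 days. SAP 16.2 drops clearance from summary statistics when extrapolation exceeds 30%, unless justified. If clearance is derived from the first interval, many values could be affected; trough is observed directly.

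**The case against.** **The dose contrast is analysed elsewhere.** The objective in protocol 2.3.1 concerns dose response. Change in eGFR and creatinine is modelled by MMRM with treatment as a factor (SAP 10.2), protocol 10.3.3 plans comparisons of each dose with placebo, and the least-squares-means statement in SAP 16.1 would print 16 against 8 mg/kg at each visit. Creatinine is also summarised by dose group with change thresholds (SAP 11.3). This stands. Where clearance is weakest, the plain dose comparison recovers most of the signal (76% against 22%). It does not use individual exposure, which is what the other endpoints get from their trough plots.

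**The power figures describe a test nobody plans.** This also stands. Protocol 10.3.6 calls for graphical exploration, and SAP 14 adds only a coefficient and a line. The figures also use AUC spread, since the documents give none for trough.

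**Trough has the same reverse-causation problem.** Within a dose, yes: if falling renal function slows elimination, trough rises as eGFR falls. But trough keeps the randomised two-fold contrast, which falling renal function cannot create. Marking points by dose lets the two be seen apart.

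**Clearance against change in eGFR has its own use.** Agreed. Protocol 3.3.2 says the effect of renal function on PK will be examined further with data from this study, so the plot should stay.

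**The catch-all for other biomarkers may already cover eGFR.** Possible, but unlikely. The opening of SAP section 10 lists creatinine and eGFR apart from biomarkers, and section 14 gives eGFR its own plot.

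**Conclusion.** The point holds for the serum exposure-response display. Clearance at Day 29 is the only serum-PK measure planned against change in eGFR, and on the protocol's figures it differs by 2% to 4% between doses while exposure doubles. An exposure-related fall in eGFR would be largely hidden in that plot.

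Two stronger readings are tempting and should be resisted. A reader might infer that such a fall cannot show at all. It can: a within-dose effect may appear as a weak positive slope, and the illustrative power on clearance is 22% to 53%, not zero. A reader might also infer that the trial has no view of dose-related renal effects. The dose-level MMRM comparisons and the urine-concentration plots provide one. Population PK/PD modelling may add to it, but it is optional.

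The conclusion about clearance rests on phase 1 dose proportionality and model predictions from healthy volunteers carrying over to this population. The size rests further on the assumed correlation of −0.40 and on predicted AUC spread standing in for trough. No endpoint, test or estimate is affected, so this is a small but worthwhile improvement to an exploratory display.

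**What to change.** In SAP section 14, add plots of change from baseline in eGFR against trough concentration at Days 29, 57, 85 and 113, in the form already planned for ACR, with points marked by dose group. Serum creatinine may be added in the same way; it is optional, because eGFR is calculated from it.

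Keep the clearance plots, and label them as addressing whether renal function affects PK. State whether the extension to all other biomarkers is meant to include eGFR and creatinine.

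Serum PK and biochemistry are both scheduled at these four visits, so no new data are needed. The cost is a few lines of SAP text and a few more descriptive plots.
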